#### 11.5 Measurement of Tumor Response

- **11.5.1** Spinal metastasis dimensions in centimeters must be recorded on the data collection forms for the initial and follow-up evaluations of the patient.
- **11.5.2** After study entry, disease evaluations will be made and recorded using the following Response Evaluation Criteria in Solid Tumors (RECIST):
  - **11.5.2.1** Complete Response (CR): No clinical evidence of disease on CT or MRI imaging.
  - **11.5.2.2** Partial Response (PR): This rating will be assigned when at least a 30% decrease in the maximum single dimension of the target lesion has occurred, taking as reference the baseline maximum dimension of the target lesion

- **11.5.2.3** Stable Disease (SD)[46]: This rating will be assigned when neither sufficient shrinkage to qualify for PR nor sufficient increase to qualify for PD, taking as reference the smallest single dimension measurement since treatment started.
- **11.5.2.4** Progressive Disease (PD): Progressive disease will be declared when at least a 20% increase in maximum dimension of the target lesion, taking as reference the smallest single dimension measurement since treatment started.

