## 4.0 Pretreatment Evaluations / Management:

Note: This section lists baseline evaluations needed before the initiation of protocol treatment that do not affect eligibility.

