#### 11.7 Removal of Subject from Study

We will be following the patients for 3 years. Subjects can be taken off the study treatment and/or study at any time at their own request, or they may be withdrawn at the discretion of the investigator for safety, behavioral or administrative reasons. The reason(s) for discontinuation will be documented and may include:

- 11.7.1 Subject voluntarily withdraws from consent
- 11.7.2 Subject is unable to comply with protocol requirements.
- 11.7.3 Subject demonstrates disease progression to targeted site.
- 11.7.4 Subject experiences toxicity that makes continuation in the protocol unsafe.
- 11.7.5 Development of second malignancy that requires treatment, which would interfere with this study.
- 11.7.6 Treating physician judges continuation on the study would not be in the subject's best interest.
- 11.7.8. Subject becomes pregnant.
- 11.7.9 If a research subject cannot be located to document survival after a period of 2 years, the subject may be considered "lost to follow-up". All attempts to contact the subject during the two years must be documented and approved by the Data Monitoring Committee.

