## Appendix I

## **STUDY PARAMETER TABLE**

	PreTreatment		During Treatment			Follow-Up (months after therapy)				
	Within 30 days of study entry		After last treatment	1	3	6	Every 6 months for three years			
Confirmation of Pathology	Х									
History/physical	Х	Х	Х	Х	Х	Х	Х			
Performance Status	Х			Х	Х	Х	Х			
MRI spine*	$X^1$			X1	X1	X 	X 			
CT spine*	$X^1$			$X^1$	$X^1$	X 	X 			
BUN, creatinine, CBC w/ platelets, PT/PTT INR	Х									
Informed consent	Х									
Tumor response evaluation	Х			Х	Х	Х	Х			
VAS at treated Site	Х		Х	Х	Х	Х	Х			
Adverse event evaluation		Х	Х	Х	Х	Х	X			
QOL Studies	Х		Х	Х	Х	Х	X			
(BPI, Fact-G, EQ-5D) Vertebroplasty	X	X 	1	x	x	x	(12 months only)			

 $*X^1$ : Per physician's discretion  $X^2$  : within one month of start of radiation treatment.

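### Read literally, the progression rule leaves the pretreatment scan out of its reference, so lesion growth before the first follow-up scan is not counted

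*Combined protocol and SAP*

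**What the plan says.** Section 11.5 of the combined protocol and SAP sets out its own response categories under the RECIST label.

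- **Partial response (11.5.2.2):** a decrease of at least 30%, "taking as reference the baseline maximum dimension of the target lesion".
- **Stable disease (11.5.2.3):** "neither sufficient shrinkage to qualify for PR nor sufficient increase to qualify for PD, taking as reference the smallest single dimension measurement since treatment started".
- **Progressive disease (11.5.2.4):** "at least a 20% increase in maximum dimension of the target lesion, taking as reference the smallest single dimension measurement since treatment started".

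Baseline is therefore named for partial response only. The baseline scan comes before treatment. The note to section 4.0 reads "This section lists baseline evaluations needed before the initiation of protocol treatment", and 4.1.3 puts the spine MRI among those evaluations. Appendix I lists the first tumor response evaluation in the pretreatment column, headed "Within 30 days of study entry".

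Section 11.2.5 schedules follow-up MRI at months 1, 3 and 6 and six-monthly after that to three years. Appendix I also shows a tumor response evaluation at month 1, but marks MRI and CT as at the physician's discretion. Section 11.7.3 lists "Subject demonstrates disease progression to targeted site" among the possible reasons for taking a subject off study.

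**The concern.** A measurement made before treatment is not, on the ordinary meaning of the words, one made after treatment started. If the pretreatment scan is excluded, the reference set is empty until the first follow-up scan. That scan then becomes its own reference, and its increase is 0% whatever the lesion has done since baseline. Growth up to that point also drops out of every later comparison, unless the lesion afterwards shrinks to or below its baseline size.

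The error runs one way: early growth at the treated site is recorded as stable or dated late. Durable local tumor control is one of the aims given for the combination in section 1.4, and these categories are the plan's only definition of tumor progression. Any description of local control drawn from them would carry the error. Two assessors who read the reference differently could also score the same lesion differently.

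**Working it through.** The plan gives no figure to reproduce here, since this is a classification rule. No sample size, power or error rate depends on it.

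**Inputs.** From the documents: the 20% PD threshold and its reference (11.5.2.4), the 30% partial-response threshold against baseline (11.5.2.2), and scans at months 1, 3, 6 and 12 (11.2.5). Lesion sizes and growth rates are my illustrations, as the documents give none.

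**Step 1: the effective threshold.** Let B be the baseline maximum dimension and B(1 + g) the smallest post-start measurement, with g > 0. Under the literal rule, PD needs a size of at least 1.2 × B(1 + g). Against baseline that is an increase of 1.2(1 + g) − 1.

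| g | Literal rule, PD threshold vs baseline | Baseline included |
|---|---|---|
| 0% | 1.2 × 1.00 − 1 = +20% | +20% |
| 10% | 1.2 × 1.10 − 1 = +32% | +20% |
| 20% | 1.2 × 1.20 − 1 = +44% | +20% |
| 30% | 1.2 × 1.30 − 1 = +56% | +20% |
| 50% | 1.2 × 1.50 − 1 = +80% | +20% |

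The literal threshold has no upper limit.

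**Step 2: a lesion that grows early and then slows.** Baseline is 3.0 cm. The literal reference is 3.9 cm from month 1 on, so PD would need 1.2 × 3.9 = 4.68 cm.

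| Month | Size (cm) | vs baseline | vs literal reference | Literal score | Baseline included |
|---|---|---|---|---|---|
| 1 | 3.9 | +30% | 0% | SD | PD |
| 3 | 4.2 | +40% | 4.2/3.9 = +7.7% | SD | PD |
| 6 | 4.4 | +47% | 4.4/3.9 = +12.8% | SD | PD |
| 12 | 4.6 | +53% | 4.6/3.9 = +17.9% | SD | PD |

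**Step 3: a lesion that grows steadily.** At rate r per month from the start of treatment, PD is declared at month t when (1 + r)^(t − 1) ≥ 1.2 under the literal rule, and when (1 + r)^t ≥ 1.2 with baseline included.

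- r = 20%: baseline included, month 1 (1.20). Literal, month 3 (1.2² = 1.44).
- r = 7%: baseline included, month 3 (1.07³ = 1.225). Literal, 1.07² = 1.145 fails at month 3 and 1.07⁵ = 1.403 passes at month 6.
- r = 3.3%: baseline included, month 6 (1.033⁶ = 1.215). Literal, 1.033⁵ = 1.176 fails at month 6 and 1.033¹¹ = 1.429 passes at month 12.

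Solving for r gives the bands in which the literal date is one scan later:

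- 20% or more per month: month 1 becomes 3.
- 1.2^(1/3) − 1 to 1.2^(1/2) − 1, about 6.3–9.5%: month 3 becomes 6.
- 1.2^(1/6) − 1 to 1.2^(1/5) − 1, about 3.1–3.7%: month 6 becomes 12.
- 1.2^(1/12) − 1 to 1.2^(1/11) − 1, about 1.5–1.7%: month 12 becomes 18.

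Between these bands, for rates above about 1.5% per month, the two rules give the same date.

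**Step 4: a lesion that first shrinks.** For 2.0 cm at baseline, then 1.6, 1.9 and 1.93 cm, the reference is 1.6 cm under both rules. The increases are 0%, 18.75% and 20.6%, scored SD, SD and PD either way.

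**The case against.** The strongest reply is that the literal reading defeats the rule. A protocol that evaluates tumor response at month 1 can hardly have meant one of its four categories to be unavailable there. Section 11.5.1 requires an initial measurement, Appendix I puts it in the same row as the follow-up values, and the criteria carry the RECIST name. The authors may well have meant a running minimum that includes the size at entry, and on that reading the problem disappears. As a statement of likely intent this has force. It does not settle the text: section 11.5.2 presents the criteria that follow as the operative ones, baseline is named for one category and not for the other two, and no other section adds it back. The source cited at stable disease, number 46, cannot help, because the reference list ends at 42.

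The reply on reach stands. Tumor response is not an objective in section 2, and 13.3 analyses only survival, functional decline and duration of pain response. Section 11.7 leaves removal to the subject's request or the investigator's discretion, and 11.7.3 does not refer to 11.5.2.4.

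A reader might also infer more than the documents support:

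- **That a short axis could serve as the reference,** so that an unchanged lesion would count as progressed. The PD rule tests an increase in maximum dimension. The phrase is naturally read as the smallest of the serial one-dimensional measurements, and the plural in 11.5.1 is explained by repeated evaluations and several treated levels.
- **That every lesion progressing by month 1 is lost.** It is not scored PD at month 1, but a lesion that keeps growing is caught at a later scan. Only one that grows less than 20% beyond its smallest post-start size is never scored PD.
- **That the bands in step 3 give an expected share of late-dated progressions.** The documents give no growth rates, so any such share would reflect the range assumed. A mean delay computed over the delayed cases alone would not describe all progressing lesions.

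**Conclusion.** The point holds as a minor correction. Under the literal wording, PD by size cannot be declared at the first follow-up scan, and the threshold against baseline rises to 1.2(1 + g) − 1. Some lesions that grow early are then recorded as stable throughout, and some that keep growing are dated one scan late.

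This rests on excluding the pretreatment scan from the reference, which is what the words say but may not be what was meant. It affects only lesions that grow before the first follow-up scan. Because follow-up imaging is discretionary in Appendix I, that scan may fall after month 1, and the uncounted interval would then be longer.

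Few patients are likely to be involved. If the 88–90% tumor control cited in sections 1.2 and 1.4 applied to the full 29 + 13 = 42 patients, 10–12% of 42, or about 4 to 5, would fail locally. Only those whose lesions grew before the first follow-up scan could be misclassified or dated late.

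The rule touches the recorded tumor-response categories and any local-control description drawn from them, and it may inform discretionary removal under 11.7.3. It does not bias any planned result: the one-month pain endpoint, both Simon designs and the 13.3 analyses do not use it.

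**What to change.** In 11.5.2.3 and 11.5.2.4, state the reference as: the smallest maximum dimension of the target lesion recorded on study, including the baseline measurement. The shrinkage half of the stable-disease definition needs no change, because it points to the partial-response criterion and so already uses baseline.

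The change is one clause in two places. It uses measurements that 11.5.1 already requires, needs no new scans or forms, and leaves lesions that first shrink scored as before. Lesions already scored under the old wording should be re-scored from the recorded dimensions so that all patients are classified by one rule. The cost is that tumor-control figures may be slightly less favourable.

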#### **11.6 Other Response Parameters**

- **11.6.1** Duration of Pain Response: The duration of pain response will be measure from the date that CR or PR was recorded to the date of increase in the VAS at the treated site to a score 2 points higher than the lowest VAS score recorded.
- **11.6.2** Time to Functional Decline: Time from study entry to a Zubrod  $PS \le 3$
- **11.6.3** Overall Survival: The survival time will be measured from the date of accession to the date of death. All patients will be followed for survival. Every effort should be made to document the cause of death.

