## Eligibility:

Inclusion:

- Patients must have localized spine metastasis (a solitary spine metastasis; two contiguous levels, or up to three separate single vertebral levels are permitted)
- Patients must have a VAS of  $\geq$ 4 at any of the planned treatment sites
- Patient with epidural, spinal nerve, and/or cord compression on MRI may be included
- Histologic confirmation of cancer is required by biopsy, prior surgery, or re-biopsy
- Narcotic pain prescription and usage information must be available and documented
- Patients must sign study specific consent
- Above the age of 18
- For women of childbearing age a negative pregnancy test is required
- Patients considered for the retreatment arm, must not of had prior radiation to the proposed spinal site within a 3 month interval prior to treatment
- Zubrod score of 0-2

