## Eligibility Checklist:

(Y) 1.	Does patient have localized spine metastasis (a solitary spine metastasis; two contiguous
	levels, or up to three separate single vertebral levels are permitted)?
(Y) 2.	Does patient have a Visual Analog Scoring of pain $\geq 4$ at any of the planned treatment
	sites within 14 days of registration? (Y) 3. Was a MRI or CT done? (Patient
	with epidural, spinal nerve, and/or cord compression on MRI/CT may be included)
(N) 4.	Does patient have paraspinal extension?
(Y) 5.	Did patients sign study specific consent form?
(Y) 6.	Is patient above the age of 18?
(Y) 7.	Does patient have a negative pregnancy test if she is at childbearing age?
(Y) 8.	Does patient have normal vertebral height?
(N) 9.	Did patient have prior radiation to the proposed spinal site within a 3 month interval prior
	to treatment if patient is considered for the retreatment arm?
(Y) 10.	Is Zubrod performance status 0-2?
(N) 11.	Has patient been non-ambulatory for more than 7 days?
(N) 12.	Does patient have spine instability requiring fixation?
(N) 13.	Is there absence of pathological diagnosis of cancer?
(N) 14.	Did patient receive chemotherapy within one week of treatment?
(N) 15.	Does patient have Multiple Myeloma, Lymphoma, or Plasmacytoma?
(N) 16.	Does the patient have a history of significant psychiatric illness?
(N) 17.	Has the patient suffered from unstable angina and/or congestive heart failure requiring
	hospitalization within the last 6 months?
(N) 18.	Has the patient had a transmural myocardial infarction within the last 6 months?
(N) 19.	Did the patient have an acute bacterial or fungal infection requiring intravenous
	antibiotics at the time of registration?
(N) 20.	Has the patient had hepatic insufficiency resulting in clinical jaundice and/or
	coagulation defects?
(Y) 21.	Is PT within normal limits or planned and feasible to be corrected to normal limits prior
	to vertebroplasy?
(Y) 22.	Is PTT within normal limits or planned and feasible to be corrected to normal limits prior
	to vertebroplasy?
(Y) 23.	Is platelet count $\geq$ 50,000?
(Y) 24.	Is narcotic pain prescription and usage information available?
	· ·

The Eligibility Checklist must be completed in its entirely prior to registration. The completed, signed, and dated checklist used at study entry must be retained in the patient's study file and will be evaluated during an audit.

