#### 3.0 Patient Selection:

3.1 All patients must be willing and capable to provide informed consent to participate in the protocol.

- 3.2 Histologic confirmation of cancer will be required by biopsy, prior surgery, and re-biopsy at the discretion of the treating physician.
- 3.3 The patient's Zubrod performance status must be 0-2
- 3.4 Patients must be or have been ambulatory within a week prior to treatment.
- 3.5 Patients with instability of the spine requiring instrumentation as judged by a neurosurgeon are not eligible.
- 3.6 No planned systemic treatment is allowed within one week after treatment.
- 3.7 Patients must have localized spinal metastasis. This includes patients with a solitary lesion, a lesion that spans two contiguous levels, a lesion with a para-spinal component, and up to three separate single vertebral levels.
- 3.8 Patients with loss of normal vertebral height, due to for example compression fracture or other process, prior to treatment are not allowed. Patients with normal height and compression fracture are allowed.
- 3.9 Patients with prior fractionated radiation to the treated site are allowed. Their prior treatment plan with date, fractionation, dose and treatment fields must be obtained. There must be at least a three month interval elapsed from the prior radiation to the treated site and enrollment.
- 3.10 Patients must have had a visual analog scoring of pain  $\geq$ 4 at the planned treated site within 14 days of registration. Pain must be ongoing or require narcotic pain medicine to control.
- 3.11 Narcotic pain prescription and usage information must be available and documented.
- 3.12 Radiation sensitive histology such as lymphoma, myoloma, or plasmacytoma are not allowed.
- 3.13 Patients must be past their 18th birthday at time of registration.
- 3.14 Women of childbearing age must have documentation of a negative pregnancy test and agreed that they or their partner use an effective contraceptive method such as condom/diaphragm and spermacidal foam, non-stainless-steel intrauterine device, or prescription birth control pills.
- 3.15 Patients should not have a history of significant psychiatric illness.
- 3.16 Patients should not have severe, active co-morbidity that would preclude vertebroplasty or stereotactic radiotherapy, defined as follows:

3.16.1 Unstable angina and/or congestive heart failure requiring hospitalization within the last 6 months.

3.16.2 Transmural myocardial infarction within the last 6 months.

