#### **13.3 Secondary Endpoints**

Secondary endpoints will be analyzed by the following methods. For overall survival Kaplan-Meier plots and median times will be reported. Time to functional decline will me measured with Kaplan-Meier plots and median times will be reported. Duration of pain response will be measured with Kaplan-Meier plots and median duration of pain response will be reported.

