#### **ZUBROD PERFORMANCE SCALE**

- 0 Fully active, able to carry on all predisease activities without restriction (Karnofsky 90-100).
- 1 Restricted in physically strenuous activity but ambulatory and able to carry work of a light or sedentary nature. For example, light housework, office work (Karnofsky 70-80).
- 2 Ambulatory and capable of all self-care but unable to carry out any work activities. Up and about more than 50% of waking hours (Karnofsky 50-60).
- 3 Capable of only limited self-care, confined to bed or chair 50% or more of waking hours (Karnofsky 30-40).
- 4 Completely disabled. Cannot carry on self-care. Totally confined to bed or (Karnofsky 10-20).
- 5 Death (Karnofsky 0).

Pain slows healing. Help us keep your pain controlled. We want you to be as comfortable as possible.

[figure not shown]
El dolor retarda la curación. Ayúdanos a controlar su dolor. Queremos que se encuentre lo más confortable que pueda.

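### Time to functional decline is defined as reaching Zubrod PS ≤ 3, which every eligible patient (PS 0-2) already meets at entry

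*Combined protocol and SAP*

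**What the plan says.** Section 11.6.2 (Other Response Parameters) gives the definition as "Time to Functional Decline: Time from study entry to a Zubrod" PS ≤ 3. Section 13.3 lists the endpoint among the secondary endpoints and fixes its analysis: "Time to functional decline will me measured with Kaplan-Meier plots and median times will be reported".

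The entry range appears in three places. Section 3.3 says "The patient's Zubrod performance status must be 0-2", the Schema's inclusion list says "Zubrod score of 0-2", and item 10 of the Eligibility Checklist, which must be answered yes, asks "Is Zubrod performance status 0-2".

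The Zubrod scale in the appendices sets the direction. Grade 0 is "Fully active, able to carry on all predisease activities without restriction", grade 3 is "Capable of only limited self-care, confined to bed or chair 50% or more of waking hours", and grade 5 is death.

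No other section restates or corrects the threshold, for example as PS ≥ 3 or as worsening from baseline.

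**The concern.** A time-to-event endpoint needs patients who are free of the event when the clock starts. Here the clock starts at study entry, and the event is a set of performance grades that contains every grade allowed at entry. The rule also runs against the endpoint's name: the better grades count as decline and the two worst do not.

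The plan commits to reporting a curve and a median from this rule. Either the rule is followed and the result carries no information, or the analyst replaces it with another. Several replacements are possible (PS ≥ 3, PS exactly 3, any worsening from baseline, with or without death), and they need not give the same median. If the choice is made once the data are in view, the endpoint is no longer pre-specified.

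**Working it through.** The documents give no event count, median or decline rate for this endpoint, so there is no stated figure to reproduce. The check is a logical one, followed by the Kaplan-Meier estimate that the rule implies.

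**Inputs**
- Event rule: PS ≤ 3, timed from study entry (section 11.6.2).
- Eligible grades at entry: {0, 1, 2} (section 3.3, Schema, Eligibility Checklist).
- Scale: {0, 1, 2, 3, 4, 5}, with 0 best and 5 death (appendix).
- Planned numbers: 29 in the single-fraction group (section 13.1) and 13 in the five-fraction group (section 13.2), so 29 + 13 = 42.

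**Step 1. Which grades count as events?** Under PS ≤ 3 they are {0, 1, 2, 3}. Grades {4, 5} do not count.

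**Step 2. Who has the event at entry?** {0, 1, 2} lies wholly within {0, 1, 2, 3}, so the probability of an event at time 0 is 1 for every eligible patient.

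**Step 3. Kaplan-Meier estimate at time 0**, S(0) = 1 − events/at risk:
- Single fraction: 1 − 29/29 = 0, median 0.
- Five fractions: 1 − 13/13 = 0, median 0.

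Early stopping changes nothing. With only the first-stage patients, S(0) is 1 − 9/9 = 0 and 1 − 6/6 = 0.

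**Step 4. Does a lenient reading help?** Suppose only assessments after entry count. Appendix I schedules PS at 1, 3 and 6 months and then every 6 months for three years. A patient with PS 0-3 at month 1 would then have the event at month 1, so the time would reflect the visit calendar. A patient who had fallen to PS 4 by month 1 and stayed there would remain event-free, and death would never count. The endpoint would still be inverted.

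**Step 5. Reverse the sign.** Under PS ≥ 3 the event grades are {3, 4, 5}. Their overlap with {0, 1, 2} is empty, so the probability of an event at entry is 0 and S(0) = 1 in both groups. With no decline rate in the documents, the median under the corrected rule cannot be projected.

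**The case against.** The strongest reply is that this is an obvious slip with little reach. The endpoint is called functional decline, the appendix shows the direction of the scale, and an analyst who found an event in every patient on day 0 would recognise the error. The endpoint is not among the secondary objectives in section 2.2, it carries no hypothesis or power, and no data are lost because PS is collected anyway. All of that stands, but it concerns how far the error reaches. It does not make the written rule usable, and section 13.3 does commit to reporting the result.

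A second reply is that PS ≥ 3 is an inference, and that counting death turns the endpoint into decline-free survival, with overall survival already defined separately in 11.6.3. The inference is the natural one, and counting death follows from the protocol's own coding of death as grade 5. It is fair, though, that sections 11.6.2 and 13.3 give no rule for death or censoring, so correcting the symbol should be accompanied by a sentence on both.

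A third is that the claim rests on a symbol read by machine from a PDF. The source page is worth checking. A general swap of signs is unlikely: section 6.4.3 has both a lower and an upper limit in one sentence, each sensible, and the platelet limit in 3.17.3 and the scan-spacing limit in 6.4.1 also read correctly.

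**Conclusion.** The definition in section 11.6.2 is wrong as written. All 42 planned patients meet the event at entry, the median time to functional decline is 0 in both groups, and true decline is either not a new event (PS 3) or not an event at all (PS 4 and 5). With the sign reversed, none has the event at entry.

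This rests on three things: the inequality reads as printed in the text supplied, patients enter with PS 0-2 as required, and the appendix scale governs. The damage is limited to one descriptive secondary endpoint. The one-month pain response, the sample sizes and the two-stage stopping rules do not depend on it. The planned analysis still cannot give an interpretable result until the definition is corrected.

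**What to change.** Amend section 11.6.2 to define time to functional decline as the time from study entry to the first Zubrod PS of 3 or more. Add a sentence stating that death counts as an event, in line with grade 5 of the appendix scale, and that patients without the event are censored at their last performance-status assessment. Keep the Kaplan-Meier plot and median in section 13.3. Make the change before this endpoint is examined, and confirm the symbol against the source page at the same time.

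The cost is one symbol and one sentence. Appendix I already schedules PS before treatment, at 1, 3 and 6 months, and every 6 months for three years. PS is not marked in the column after the last treatment, and the 2-week visit in section 11.2.1 has no column there, but the corrected definition does not need either. No sample size changes.
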